15.3.11 Safety follow-up

SAEs and AEs of special interest will be collected during 6 months after the last vaccination through telephone calls approximately every 8th week ± 7 days following the last visit to the clinic for a total of 3 occasions (see Section 14.1.5).

The following will be collected:

- pIMDs, i.e. a subset of AEs that include both clearly autoimmune diseases and also other inflammatory and/or neurologic disorders which may or may not have an autoimmune aetiology.
- SAEs

15.3.12 Reporting period for adverse events

Collection of pre-dose events starts after the subject has signed the ICF and continues until the first administration of IMP.

Collection of AEs starts upon administration of the first dose of IMP and continues until the subject's last visit to the clinic (Visit 4 for group 1 to 4 and Visit 3 for group 5 and 6).

Any apparent side effects experienced by the subject will be assessed from the time the subject signs the informed consent and throughout the last visit to the clinic.

In addition, SAEs and AEs of special interest will be documented during the 6 months follow-up period (Section 15.3.11).

15.3.13 Follow-up on adverse events (serious and non-serious)

All AEs collected during the reporting period until the subject's last visit to the clinic and which are assessed as possibly or probably related to the IMP must be followed until resolution or until assessed by the Investigator as stable.

All SAEs collected during the reporting period until the subject's last visit to the clinic must be followed up until the subject has recovered, stabilised or recovered with sequelae. The Investigator must report to the Sponsor all relevant new information. Relevant information includes discharge summaries, autopsy reports and medical consultation.

SAEs that occur during the 6 month safety follow-up period and that are assessed by the Investigator or medical monitor as possibly or probably related to the IMP must be followed up until the subject has recovered, stabilised or recovered with sequelae.

15.4 PREGNANCY

A pregnancy in itself will not be considered an SAE. If a subject becomes pregnant during the study treatment period (including 2 months after the last vaccination), the pregnancy should be reported to PCG and the Sponsor using the pregnancy report form. The subject and offspring must be monitored for AEs during the entire pregnancy. Any AE occurring to the offspring during the pregnancy or at birth must be reported.

In case of spontaneous abortion, stillbirth, congenital anomaly or birth defect, death or any other serious infant condition, the event should be reported as an SAE according to the procedures described in 15.3.9.

15.5 LABORATORY SAFETY ASSESSMENTS

Blood samples for analysis of clinical chemistry and haematology parameters will be collected by venepuncture at visits specified in Table 1 and Table 3. Samples will be analysed using routine methods at the local hospital.

Urine analysis will be performed at the clinic using dipsticks.

The following safety laboratory parameters will be measured:

Clinical chemistry (serum)

Urea nitrogen
Creatinine
Total protein
Total bilirubin
Alanine aminotransferase (ALT)
Aspartate aminotransferase (AST)
Alkaline phosphatase
Gamma-glutamyl transferase (GGT)
Creatinine phosphokinase (CPK)
C-reactive protein (CRP)

Urine analysis:

pH
Glucose
Ketones
Nitrites
Blood
Leukocytes

Haematology:

White blood cell count (WBC) and differential
(neutrophils [% abs], lymphocytes [% abs],
monocytes [% abs], basophils [% abs])
Haemoglobin
Red blood cell count (RBC)
Platelet count

15.6 PROCEDURES FOR BIOLOGICAL SAMPLES

The anticipated total volume of blood that will be drawn from each subject during the study will not exceed 150 mL per subject, which is less than half the volume drawn during a regular blood donation.

15.6.1 Chain of custody for biological samples

A full chain of custody is maintained for all samples throughout their lifecycle.

The study site will keep full traceability of collected biological samples from the subjects while in storage at the research clinic until shipment and keeps documentation of receipt of arrival.

The sample receiver (the analytical laboratory or process laboratory) will keep full traceability of the samples while in their storage and during use until used, shipped or disposed of.

The Sponsor will keep oversight of the entire life cycle through internal procedures, monitoring of study sites and auditing of external laboratory providers as applicable.

15.7 PHYSICAL EXAMINATION

A physical examination will be performed at the time points specified in Table 1 and Table 3 and will cover the following body systems: ear, nose and throat, cardiovascular system, pulmonary system, skin, abdomen and neurological system.

It will be recorded in the eCRF if any abnormalities were observed in the physical examinations. Any abnormalities will be specified and documented as clinical significant or not clinically significant. Any post-dose clinically significant findings will be recorded as AEs.

15.8 VITAL SIGNS

Systolic and diastolic blood pressure and heart rate will be measured in supine position after 10 minutes rest at visits and time points specified in Table 1 and Table 3. The blood pressure will be measured using an arm cuff of appropriate size. Body temperature will be measured orally using a digital thermometer.

15.9 12-LEAD ECG

12-lead ECG will be recorded in supine position after 10 minutes rest at time points specified in Table 1 and Table 3. Any abnormalities will be specified and documented as clinically significant or not clinically significant. Any post-dose clinically significant ECG findings will also be reported as AEs.

15.10 INFLUENZA TEST

Subjects who develop suspected influenza during the study period should be tested using a diagnostic test at the discretion of the Investigator.

Influenza testing will be performed at Klinisk mikrobiologi (Uppsala, Sweden) according to standard procedures.

16. EFFICACY ASSESSMENTS

16.1 NASAL SWAB

Nasal swab will be performed at visits and time points specified in Table 1 to Table 4. Briefly, nasal swab samples will be obtained from both nares of subjects by sampling with a cotton-tipped wooden swab that has been premoistened with sterile phosphate buffered saline (PBS). The swab will be placed into the anterior nares and rolled across the mucosa for a few seconds with moderately constant pressure. The swab will then be placed in a small volume of PBS and vigorously shaken and wrung out. Samples will be frozen before shipment to Vismederi (Siena, Italy) for IgA analysis. Procedure specific details will be described in a separate document.

16.2 IMMUNOLOGY BLOOD SAMPLING

Blood sampling for analysis of influenza-specific immune responses will be performed according to standard methods at visits and time points specified in Table 1 to Table 4. Details of the sampling procedures will be described in a separate laboratory manual.

Blood samples allocated for antibody analysis will be centrifuged and the serum will be frozen. Serum samples will be shipped to Vismederi (Siena, Italy) for analysis of HI and VN titres and possibly also for SRH and NA-specific antibodies.

Blood samples for T-cell analysis will be shipped to the Rudbeck Laboratory (Uppsala, Sweden) for PBMC preparation. PBMCs will subsequently be shipped to Vismederi (Siena, Italy) for T-cell analysis.

17. DATA MANAGEMENT

Data management based on GCP refers to the activities defined to achieve safe routines to efficiently enter subject information into a database, avoiding errors.

The data management activities, such as procedures for data validation, will be described in a separate data management plan (DMP). The eCRF will be designed in accordance with the CSP.

17.1 THE WEB-BASED ECRF

Clinical data (including AEs and concomitant medications) will be entered into a 21 CFR Part 11-compliant eCRF (Viedoc™) provided by PCG. The eCRF includes password protection and internal quality checks, such as automatic range checks, to identify data that appear inconsistent, incomplete,

or inaccurate. Clinical data will be entered directly from the source documents, which are to be defined at each site before inclusion of the first subject.

Authorized study site personnel designated by the Investigator will complete data collection. Appropriate training and security measures will be completed with the Investigator and all authorized study site personnel prior to the study being initiated and any data being entered into the system for any subject.

Captured data will be monitored electronically. Source data review and source data verification (SDV) will be performed at the site as described in the monitoring guidelines. Any inconsistencies will be presented as queries, either as automatically generated queries if raised by the logical data checks of the eCRF system, or by manually generated queries if raised by the off line data validation checks or the data review performed by e.g. the monitor. Queries shall be resolved in a timely manner by a trained member of the site staff.

17.2 ENTERING OF DATA INTO THE ECRF

All data must be entered in English. The eCRFs should always reflect the latest observations made during the subjects participating in the study. Therefore, the eCRFs should be completed as soon as possible during or after the subject's visit. To avoid inter-observer variability, every effort should be made to ensure that the same individual who made the initial baseline determinations completes all corresponding safety evaluations.

The Investigator must verify that all data entries in the eCRFs are accurate and correct. If some assessments are not done, or if certain information is not available, not applicable or unknown, the Investigator should indicate this in the eCRF. The Investigator will be required to electronically sign off the clinical data.

17.3 THE QUERY PROCESS

The monitor will review the eCRFs and evaluate them for completeness and consistency. The eCRFs will be compared with the respective source documents to ensure that there are no discrepancies between critical data in accordance with the monitor guidelines.

All entries, corrections, and alterations are to be made by the Investigator or designee. The monitor cannot enter data in the eCRFs. Once clinical data have been submitted to the central server via the eCRF, corrections to the data fields will be audit trailed, meaning that the reason for change, the name of the person who made the change, together with time and date will be logged. Roles and rights of the site personnel responsible for entering clinical data into the eCRF will be determined in advance. If additional corrections are needed, the responsible monitor or project manager will raise a query in the electronic data capture application.

The appropriate investigational personnel will answer the queries in the eCRF. This will be audit trailed by the electronic data capture application meaning that the name of investigational personnel, time, and date is logged.

The data from the eCRFs will be sent to the Sponsor and a copy will be sent to each clinic for filing in the Investigator site file after finalization of the CSR.

17.4 SOURCE DOCUMENTS

Data entered into the subjects medical record at the clinic will be considered as the source data and will be transferred to the relevant sections of the eCRF. Source documents are all documents used by the Investigator or hospital that relate to the subject's medical history, that verifies the existence of the subject, the inclusion and exclusion criteria, and all records covering the subject's participation in the study. Source documents include laboratory notes, memoranda, material dispensing records, subject files, etc.

The eCRF is considered as source data when data is entered directly into the eCRF.

The Investigator is responsible for maintaining source documents. These will be made available for inspection by the monitor at each monitoring visit. All supportive documentation submitted with the eCRF, such as laboratory or hospital records, should be clearly identified with the study ID and subject number. Any personal information, including name, should be removed or rendered illegible to preserve individual confidentiality.

17.5 USER ID

The eCRF records will be automatically appended with the identification of the creator, by means of their unique UserID. Specified records will be electronically signed by the investigator to document his/her review of the data and acknowledgement that the data are accurate. This will be facilitated by means of the Investigator's unique UserID and password; date and time stamps will be added automatically at time of electronic signature. If an entry in an eCRF requires change, the correction should be made in accordance with the relevant software procedures.

17.6 AUDIT TRAIL

All changes made to data entered in the eCRF will be fully recorded in a protected audit trail, and a reason for the change will be required.

Once all data have been entered, verified, and validated, the database will be locked.

18. STATISTICS

18.1 STATISTICAL ANALYSIS PLAN

A Statistical analysis plan (SAP) will be prepared and finalised prior to the code-breaking of the subjects' treatment. This document will provide further details regarding the definitions of analysis variables and analysis methodology to address all study objectives.

A blinded data review will be conducted prior to code-breaking of the subject's treatment assignment. This review will assess the accuracy and completeness of the study database, subject evaluability, and appropriateness of the planned statistical methods.

18.2 SAMPLE SIZE DETERMINATIONS

A total of 162 subjects are planned to be randomised in a 2:1 ratio to treatment groups 1 to 3 or treatment groups 4 to 6, respectively (Table 5). The sample sizes are not based on statistical criteria with a power calculation but on what is assessed adequate based on previous experience in similar studies. Sample sizes are larger in the groups receiving antigen alone or antigen with Endocrine since the evaluation of the effect of Endocrine on safety/tolerability and immune response compared with no Endocrine is a key objective.

18.3 DATABASE LOCK

After all subjects have completed the last visit to the clinic (visit 4 group 1 to 4, and visit 3 group 5 and 6), a clean file meeting will take place and an unblinded analysis of all data (baseline data, efficacy data and safety data) collected during the clinical phase will be conducted. The outcome of the analyses will be documented in a full ICH-E3 compliant CSR.

An additional clean file meeting will be conducted after completion of the last telephone follow-up call prior to final database lock. Data from the safety follow-up period will be summarised in an addendum to the CSR.

18.4 ANALYSIS SETS

The classification of subjects to each analysis set will be decided at the first clean file meeting prior to database lock. The classification will be documented in the clean file protocol and in the CSR.

18.4.1 Full Analysis set

The full analysis set (FAS) is used to describe the analysis set that is as complete as possible and as close as possible to the intention-to-treat (ITT). The FAS will consist of all randomised subjects who received at least one dose of study medication and have at least one post-randomisation efficacy assessment.

The FAS analysis will be the primary analysis for evaluation of immune response and immunology efficacy data and will be performed for all efficacy endpoints unless otherwise stated. Subjects will be analysed according to the treatment group to which they were randomised.

18.4.2 Per-protocol Analysis Set

The per-protocol analysis set (PPAS) is a subset of the FAS and consists of all subjects without any major protocol deviations, i.e. a set of subjects that participated in the study as intended.

Analysis based on the PPAS will be used to assess the robustness of the results from the FAS analyses. Subjects will be analysed according to treatment which they received.

Subjects diagnosed with influenza after start of treatment will not be included in the PPAS.

18.4.3 Safety Analysis Set

The safety analysis set will consist of all subjects who received at least one dose of study medication. The safety analysis set will be used for evaluation of safety data. Subjects will be analysed according to the treatment which they received.

18.5 STATISTICAL METHODS

18.5.1 Demographics and other baseline characteristics

Subject disposition will be presented for all enrolled subjects (including screening failures). The number and percentage of randomised subjects who completed the study and discontinued from the study will be provided, as well as reasons for early discontinuation. The reasons for screening failures will also be summarised.

Demographic information and baseline characteristics will be summarised by treatment group and in total for the following:

Demographics

- Age (years);
- Height (cm);
- Weight (kg);
- BMI (kg/m²)
- Gender (male/female).

Medical history and concurrent diseases;

Prior and concomitant medications.

18.5.2 Safety analysis

Incidences will be descriptively compared between the treatment groups. For categorical variables the frequency and proportion will be presented. Percentages will be based on the number of subjects with evaluable data within each treatment group. Continuous variables, including change

from baseline, will be presented using appropriate descriptive statistics. Safety analyses will be based on the safety analysis set.

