Immunose FLU has been shown to induce complete protection in influenza-naïve ferrets challenged with influenza virus. Virus neutralising titres were similar to what has been shown with Fluenz in the ferret model and support the paediatric profiling of Immunose FLU. Immunose FLU also induces high haemagglutination inhibition (HI) antibody titres in influenza-naïve ferrets already after one vaccine dose.

Nasal vaccination has the potential to elicit both systemic and mucosal immunity against pathogens. However, split and subunit vaccines lack potency to stimulate mucosal immunity, and a nasal adjuvant is indispensable for eliciting a potent mucosal immune response to nasal vaccines. Adjuvants are substances that are added to a vaccine antigen in order to enhance the immunological response. Immunose FLU is composed of inactivated split influenza antigen combined with Eurocine Vaccines' proprietary adjuvant Endocine. [REDACTED]

[REDACTED] The two lipids in Endocine are naturally present in human adipose tissue. Both [REDACTED] and [REDACTED] are approved for pharmaceutical use and are described in the European and US Pharmacopoeia.

In the present study, the safety and tolerability and the immune response to intranasally administered Immunose FLU based on Endocine in 2 doses (1% and 2%) and quadrivalent influenza antigens will be evaluated in adults. One group receiving influenza antigen without Endocine and one group receiving saline alone, both for intranasal administration, are included to enable evaluation of the Endocine effect on the immune response and the safety and tolerability of Endocine compared to influenza antigen alone and to placebo. In addition, one group will receive [REDACTED] and one group will receive [REDACTED], for a general comparison of the safety and tolerability and the immune response of Immunose FLU with that of these marketed products.

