9.5 RATIONALE FOR THE STUDY DESIGN, DOSES AND CONTROL GROUPS

Immunose FLU with 2 different concentrations of Endocine will be investigated to assess the influence of adjuvant concentration on the response parameters, whereas the antigen dose will be kept constant according to standard practice for influenza vaccinations. The inactive control group (saline) is included for an enhanced interpretation of safety data through control for placebo effects, and for the analysis of immune responses through control for background antibody levels. The comparators to Immunose FLU; ██████████ for intranasal administration and ██████████ for intramuscular injection of antigen have been selected to compare the safety and tolerability and the overall immune response.

Immunose FLU will be administered at 2 occasions with a 3-week interval to maximize the magnitude of the immune response as indicated by non-clinical data. Influenza antigen without adjuvant and saline alone will also be administered nasally at two occasions. ██████████ and ██████████ will be administered at one occasion according to the prescribing information.

Endocine will be tested at the concentrations 1% and 2% in two different treatment groups. In a previous study with nasal influenza vaccination, Endocine was evaluated with concentrations ranging from 0.5% to 2% (report EV 2011-08, EUR-001). Local tolerability symptoms were more commonly reported following vaccination with Endocine compared to vaccination without Endocine with a slightly higher incidence of reactions following administration of 2% compared to 0.5% and 1%. Symptoms were rapidly reversible and there were no safety concerns for any treatment group. In the present study the dose-response for Endocine versus safety variables and immune response will be evaluated, and the dose steps 1% and 2% are considered adequate.

The immunology variables to be investigated in the study have been selected to represent both systemic and local immune responses, which both might be indicative of the protective efficacy in later studies.

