10.1.1 Primary endpoints

- Type and incidence of AEs and SAEs from the time of first study drug administration (Visit 2) until the last visit to the clinic (Visit 4 for group 1 to 4 and Visit 3 for group 5 to 6).
- Type and incidence of SAEs and AEs of special interest during the 6 months safety follow-up.
- Frequency and severity of administration-site reactions as assessed by an independent evaluator with help from study subject before study drug administration and 15 minutes and 120 minutes after study drug administration. Administration-site reactions to be recorded are swelling, redness, pain and pruritus in the administration area (nose or arm). Reactions are classified as none, mild, moderate or severe. The administration-site reactions pain and pruritus will also be recorded by the subject in an electronic diary for 10 days starting in the evening the day after each treatment and classified as none, mild, moderate or severe.
- Frequency of solicited AEs. The subjects will record the occurrence of solicited AEs in an electronic diary for 10 days after study drug administration. Solicited AE include runny nose, nasal congestion, sneezing, fever (i.e., temperature >38°C), chills, sweating, headache, tiredness, muscle aches, joint pain, cough, sore throat, nausea.
- Frequency of clinically significant changes in ECG, vital signs, physical examination findings and laboratory variables from baseline to the last visit to the clinic.

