13.5 DOSES AND TREATMENT REGIMENS

13.5.1 Doses and treatment regimens group 1 to 4 (test products)

The test products (Immunose FLU, influenza antigen and saline, respectively) will be administered in 2 doses delivered at least 3 weeks apart. Up to 4 weeks between administrations is allowed.

A short instruction for nasal administration of Immunose FLU, influenza antigen and saline is provided below and a complete instruction is provided separately.

Prior to administration, the content of each vial should be mixed carefully. Upon administration, the subject should sit in an upright position and lean the head backwards (Figure 2 and Figure 3). A calibrated pipette and pipet tips must be used.

A total of 150 µl of IMP should be administered in each nostril. The nose drops must be applied on the upside nasal cavity.

Figure 2 Head position of subject upon nasal administration of test products (group 1 to 4)

Figure 3 Administration of test products (group 1 to 4)

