13.5.2 Doses and treatment regimens group 5 and 6 (comparators)

The comparators ([REDACTED]) will be administered as a single dose according to the manufacturer's instructions.

[REDACTED] will be administered [REDACTED]

[REDACTED] will be administered [REDACTED]

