18.5.2.1 Adverse Events

All AEs will be coded using the medical dictionary for regulatory activities (MedDRA). Data will be summarised using preferred term (PT) and primary system organ class (SOC) and presented by treatment group and in total.

Nature, incidence, severity and the Investigator's causality assessments will be reported for each AE. AEs, SAEs, drug-related AEs, AEs leading to withdrawal and AEs of special interest will be listed and summarised by incidence and treatment group.

Pre-treatment events, collected from the signing of the ICF until the first dose, will be listed and summarised by incidence and treatment group.

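### AE incidence covers two doses and 42–49 days in Groups 1–4 but one dose and 21–28 days in Groups 5–6, and no common-window or per-dose AE table is specified for the comparison with the marketed vaccines

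*Combined protocol and SAP*

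**What the plan says.** Section 10.1.1 makes the type and incidence of AEs a primary endpoint, counted from first administration "until the last visit to the clinic (Visit 4 for group 1 to 4 and Visit 3 for group 5 to 6". Section 15.3.12 uses the same limits: "Collection of AEs starts upon administration of the first dose of IMP and continues until" the last clinic visit.

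Section 11 puts Visit 3 at Day 21 (+7) and Visit 4 at Day 42 (+7). Under Section 13.5.1 the Group 1–4 products "will be administered in 2 doses delivered at least 3 weeks apart". Under Section 13.5.2 each comparator "will be administered as a single dose".

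For analysis, Section 18.5.2 says: "Incidences will be descriptively compared between the treatment groups". Percentages use subjects with evaluable data in each group as the denominator. Section 18.5.2.1 adds that AEs, SAEs, drug-related AEs, AEs leading to withdrawal and AEs of special interest "will be listed and summarised by incidence and treatment group". Sections 18.5.2 to 18.5.2.3 name no per-dose, per-period, common-window or exposure-adjusted AE table.

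The comparison is intended. Section 9.1 includes Groups 5 and 6 "for a general comparison of the safety and tolerability and the immune response of Immunose FLU with that of these marketed products", and Section 9.5 says that the comparators "have been selected to compare the safety and tolerability and the overall immune response". Section 18.1 leaves further analysis detail to a SAP finalised before code-breaking. The text reviewed here contains no such SAP, so this point concerns what Section 18 itself specifies.

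**The concern.** A per-subject incidence can only grow as doses and days are added. If two products carry the same risk per dose period, the group followed through two periods is expected to show an incidence at least as high as the group followed through one, and strictly higher unless exactly the same subjects react both times.

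The imbalance also enters through solicited data. Moderate or severe clinic reactions (Section 15.1) and diary reactions (Section 15.2) are reported as AEs. Groups 1–4 have two dosing visits and 20 diary days; Groups 5–6 have one dosing visit and 10 diary days.

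At stake is how the Immunose FLU groups look beside the marketed vaccines on a primary endpoint. The tilt runs against the sponsor's own product. No test or error rate is involved, because the safety comparison is descriptive.

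**Working it through.** **Inputs from the protocol.** Group sizes are 36, 36, 36, 18, 18 and 18 (Section 13.7.1). The last AE day is 42–49 in Groups 1–4 and 21–28 in Groups 5–6 (Sections 10.1.1 and 11). Doses are 2 and 1 (Sections 13.5.1 and 13.5.2). The diary runs 10 days per treatment (Section 15.2).

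**The plan's own figures.** There is no power calculation to reproduce. The total agrees: 3 × 36 + 3 × 18 = 162. The stated durations agree with the schedule tables: (42 + 201 + 7)/7 = 35.7, i.e. 36 weeks for Groups 1–4; (42 + 180 + 7)/7 = 32.7, i.e. 33 weeks for Groups 5–6.

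**Observation time.** The ratio is 42/21 = 2.0 at nominal visit days, with limits 42/28 = 1.5 and 49/21 = 2.33.

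**Two equally tolerated products.** The documents give no AE rate, so everything from here is assumed. Let p be the risk of at least one AE in a dose period, the same in both products and both periods, and r the within-subject correlation between periods. One-period incidence is p. Two-period incidence is 2p − [p² + r·p(1 − p)].

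| p (one period) | two periods, r = 0 | r = 0.5 | r = 1 |
|---|---|---|---|
| 10% | 19.0% (ratio 1.90) | 14.5% (1.45) | 10% (1.0) |
| 20% | 36.0% (1.80) | 28.0% (1.40) | 20% (1.0) |
| 30% | 51.0% (1.70) | 40.5% (1.35) | 30% (1.0) |
| 40% | 64.0% (1.60) | 52.0% (1.30) | 40% (1.0) |
| 50% | 75.0% (1.50) | 62.5% (1.25) | 50% (1.0) |

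At p = 30% the excess is 21, 10.5 or 0 points. For 36 versus 18 subjects, the standard error with 30% in both arms is √[0.3 × 0.7 × (1/36 + 1/18)] = 13.2 points, so these are 1.6, 0.8 and 0 standard errors. With 51% versus 30% the standard error is √[0.51 × 0.49/36 + 0.3 × 0.7/18] = 13.6 points, and 21 points is 1.5 standard errors.

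**Which arm looks worse.** By exact binomial enumeration over p = 10% to 50%, with equal products and independent periods, the 36-subject arm shows the higher observed percentage with probability 0.79 to 0.96. At r = 0.5 it is 0.65 to 0.78. In a common one-dose window it is 0.45 to 0.46 (below one half because of ties).

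**How much is extra observation time.** Take p = 30% and independence, and split the period risk into a dose-related part d and a background part b, with (1 − d)(1 − b) = 0.7. The whole regimen gives 1 − (1 − d)²(1 − b)² = 51%. Two doses with only one background period give 1 − (1 − d)²(1 − b).

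| b | two doses, one background period | extra background time | second-dose burden |
|---|---|---|---|
| 5% | 48.42% | 51 − 48.42 = 2.58 points | 18.42 points |
| 10% | 45.56% | 5.44 points | 15.56 points |
| 20% | 38.75% | 12.25 points | 8.75 points |

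**Would a first-dose-to-Visit-3 cut be matched?** On doses (one), days (21–28) and diary days (10), yes. On Visit 3 procedures, not fully. Groups 5–6 have the physical examination, ECG, blood and urine tests at Visit 3 (Section 14.1.3.2), whereas Groups 1–4 have them at Visit 4 (Section 14.1.4). Clinically significant examination and ECG findings become AEs (Sections 15.7 and 15.9), and the AE definition can cover abnormal laboratory values (Section 15.3.1). Conversely, only Groups 1–4 have a pre-dose nasal inspection, subject-rated pain and pruritus, and a temperature reading at Visit 3 (Sections 14.1.3.1 and 15.1).

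**The case against.** The strongest reply is that two doses versus one are the regimens as designed, so whole-period incidence answers a fair question, and that other planned outputs already help to read it. Much of this stands. At 5% or 10% background risk, most of the illustrated excess is second-dose burden, which is not bias. Saline Group 4 has the same two-dose schedule and shows background incidence over the longer window. The drug-related AE summary in Section 18.5.2.1 should remove part of the background, although causality in Groups 5–6 is judged open label. A reader might therefore infer that tolerability cannot be separated from exposure at all; the documents do not support that.

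It is also fair that the contrast is secondary. It has 18 subjects per comparator, is open label, and one comparator is intramuscular, so no window makes it a clean product comparison. Section 18.2 names the effect of Endocine against no Endocine as a key objective. That contrast lies within Groups 1–4, on one schedule.

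Deferral to the SAP explains why table detail is absent, but Section 18 already fixes the window and the comparison, and following them as written produces the tilt. Section 18.5.2.2 says when local reactions are evaluated. Tables by visit are a natural reading of it, but it does not state them, and it does not cover AEs or diary data.

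A stricter remedy, excluding every AE found only through a Visit 3 procedure that one side has, is tempting but not justified. The documents give no rate for such AEs and describe no field recording how an AE was detected. Such sorting would also not be blind for the open-label groups, even at the blinded data review.

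**Conclusion.** The point holds for one contrast, Groups 1–2 against Groups 5–6, and should be fixed. The unequal doses and windows are on the face of the protocol. The size is not, and rests on assumed rates: at 30% risk per period, 0 to 21 points between full correlation and independence. The split of those 21 points was worked only under independence, the highest-excess case shown: 2.6, 5.4 or 12.3 points are extra background time at 5%, 10% or 20% background risk.

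A reader might infer that the whole excess is bias, or that the safety comparison in general is compromised. Neither follows. Contrasts of Groups 1–2 with unadjuvanted antigen and saline share schedule and window, and SAE and special-interest follow-up runs for 6 months after the last vaccination in every group (Section 14.1.5).

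**What to change.** In Sections 18.5.2.1 to 18.5.2.3, or in the SAP before code-breaking:

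1. Add an AE table for all groups with onset from first dose to Visit 3 (before the second dose in Groups 1–4). Make it the main descriptive comparison of Groups 1–2 with Groups 5–6. Footnote the differing Visit 3 procedures on each side and, where the record allows, show AEs arising from them separately.
2. For Groups 1–4, tabulate AEs after the second dose, and clinic and diary reactions by dose.
3. Keep the whole-period table, labelled as a whole-regimen comparison with unequal doses and observation time, and note that Groups 5–6 are open label.

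The cost is wording and a few tables. AEs are collected both pre-dose and post-dose at Visit 3 in Groups 1–4 (Section 14.1.3.1), so events can be assigned to a period without new visits or samples. The common-window table omits second-dose events, which tables 2 and 3 show.

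A separate clerical item: Section 19.7 gives Group 4 a last visit at Visit 3, which conflicts with Sections 10.1.1, 11 and 15.3.12 and must be reconciled.
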